# 8 Safety evaluation

#### 8.1 List of safety parameters

The following parameters will be taken into account for the safety evaluation:

- AEs and/or SAEs rates per trial arms;
- Global tolerance evaluation during the trial by the Investigator and patient;
- Vital signs (heart rate, blood pressure, body temperature, breathing rate);
- ECG parameters;
- Laboratory results.

#### 8.2 Methods and timing for evaluation, recording, and analysis of safety parameters

Safety parameters are evaluated at every planned and unscheduled visit.

# **8.3** Requirements for reporting, registration, and reporting of AEs and intercurrent diseases

# 8.3.1 Definitions of adverse events and serious adverse events

Adverse event (AE) is any adverse medical event identified in a patient or a clinical trial patient after the use of the drug, which may or may not have a causal relationship with its usage. Thus, adverse event (AE) can represent any adverse symptom (including laboratory deviation from the norm), complaint, or disease, for which a temporal causal relation cannot be excluded with the use of medicinal (study) product, regardless of the presence or absence of such a relation.

Serious adverse event (SAE) represents any event, unfavorable from medical perspective, which with any dose:

- Resulted in death;
- Is life threatening;
- Results in disability/incapacity to work;
- Is a congenital anomaly or development defect;
- Requires hospitalization or its extension;
- Is significant from medical perspective: a decision whether expedited reports is feasible in other situations (e.g., in case of events important from medical perspective, which are not directly life-threatening for a

patient, do not result in death or hospitalization, but pose the patient to risk or require intervention to prevent one of the above outcomes) shall be made on the basis of medical and scientific evaluation. Such cases should be usually considered serious adverse events.

Adverse drug reaction (ADR) is any adverse event which might have causal relation to the drug in the opinion of the Investigator or Sponsor (see Section 8.3.3 below).

An unexpected adverse reaction is defined as an adverse drug reaction, the nature or severity of which is not consistent with the Reference Safety Information (e.g. SmPC, Investigator's Brochure). The term "severity" is used to describe the intensity of a specific event. This term should be distinguished from the term "serious". Reports which add significant information on specificity, increase in incidence, or severity of the known, already documented serious adverse reactions, constitute the unforeseen events.

Information about side effects already known for this study drug is available in the Investigator's Brochure. This information will be included into Patient Information Sheet, and it should be discussed with the trial subjects.

More details are given in Brief Reference Manual for filling in the Serious Adverse Event Report Form (to be provided by the Sponsor).

# 8.3.2 Intensity of AE

The term "severity" is used to describe the intensity of a specific event. This term should be distinguished from the term "serious". During the trial, the Investigator will detect adverse events and classify them by intensity as follows:

- Mild event: as a rule, is temporary and does not restrict normal daily activities;
- Moderate event: restricts normal daily activities significantly;
- Severe event: impedes normal daily activities in full.

#### 8.3.3 Causality with the study drug

The Investigator will perform evaluation of adverse events after examination of all available data. In addition, he/she will perform their repeated evaluation if new information appears. The study drug is the drug investigated during the trial, and control drug or placebo used during any phase of this trial.

All AEs spontaneously reported by volunteers or observed by the Investigator will be evaluated in accordance with the following definitions:

Suspected: temporal relation between development of clinical event and applied study drug indicates **possible presence of causality,** while other drugs, therapeutic interventions, or baseline states do not allow explaining development of this event with sufficient grounds.

Non-suspected: temporary relation between development of clinical event and used study drug **indicates for the remote presence of causality**, while other drugs, therapeutic interventions, or baseline states can be considered with sufficient grounds as explanation for observed event.

Evaluation of causality is of great significance, and it should be performed for each reported unique event and for each study drug, not being the study drug or any other concomitant drug (if appropriate). In case of no evaluation of causality available, the Sponsor will consider such events as associated with the trial therapy.

The Investigator must inform LPPV on AEs with suspected causality to the drug which is not a study drug or another concomitant drug (produced by Sandoz or other manufacturers), even if those AEs are not serious (see Section 8.3.5 for contact information).

#### 8.3.4 Documentation on adverse events

Any AE (not serious or serious), occurring after the subject has provided informed consent specific for this trial before completion of the trial, must be documented on the pages intended for adverse events in the Individual Case Record Form (ICRF).

The non-leading questions to the subjects should be used at each trial visit in order to detect AE. AEs can be also detected if the subjects report on them themselves during visits or between the visits as well as if they are found during examination, by the results of laboratory analyses or other tests. All AEs require proper treatment. Actions taken to cure AE should be documented and related to one of the following categories: "no action taken", "prescription of the drug (accompanying therapy)", or "other treatment". Besides, the actions should be documented, which were undertaken in relation to the study drug, and they should be referred to one of the following categories: "no changes", "withdrawal", "dose reduced", "dose increased", "therapy suspended", "action is unknown", and "not applicable". Concomitant therapy, other treatment methods, or changes of the study drug should be determined and documented.

The medical conditions/disorders present before the trial therapy initiation are considered to be AEs unless they get worsened after the inclusion in the trial. Abnormal laboratory or test results are considered to be AEs only if they evoke clinical signs, are clinically significant, or require therapy.

After detection of AE, it should be followed up until its resolution or until it is recognized as permanent. The event outcome should be documented and referred to one of the following categories: "event not resolved/did not change", "health status gets worse", "event resolved/subject recovered", "event improved/subject recovers", "event resolved/subject recovered", "lethal outcome", or "outcome unknown". Evaluation of AE should be performed during each visit (or more frequently, in case of any indications) for any changes in severity, suspected association with the study drug, interventions undertaken for its treatment, and outcome.

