#### Secondary goals:

- Assessment of safety of Angal, lozenges [menthol], 1 mg + 5 mg (Sandoz d.d., Slovenia) administration of 1 lozenge with a not less than 2-hour interval, up to 6–10 times per day, for 4 days or until full recovery (whichever occurs first during 4 days of therapy), compared to ANTI-ANGIN® FORMULA, lozenges, 0.2 mg + 2 mg + 50 mg (OOO Valeant, Russia)—administration of 1 lozenge with a not less than 2-hour interval, up to 6 lozenges per day, for 5 days or until full recovery (whichever occurs first during 5 days of therapy) in the treatment of patients with uncomplicated acute Infectious and inflammatory diseases of the pharynx accompanied by a sore throat.
- Evaluation of adverse events (AEs) in the trial arms.
- The AEs rate comparison between the trial arms.

S. SANDOZ

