#### 5 Selection and exclusion of the subjects

#### 5.1 Inclusion criteria

The patients who meet all the inclusion criteria listed below will be included in the trial:

- 1. The Informed Consent Form voluntarily signed by the patient.
- 2. Men and women at the age of 18 to 45 years old, inclusively.
- 3. A diagnosis of acute, uncomplicated, inflammatory and infectious condition of the pharynx associated with the inflammation and pain in the throat.
- 4. Manifestation of the first signs of acute, uncomplicated, inflammatory and infectious condition of the throat (pharyngitis and/or tonsillitis) not more than 48 hours before the inclusion.
- 5. A baseline total sum of TSS (Tonsillopharyngitis Severity Score) points  $\geq$ 5.
- 6. Body temperature measured in the axillary cavity is less than 37.5 °C.
- 7. Women with childbearing potential should demonstrate a negative pregnancy test result at screening (except for the women after surgical sterilization or menopause for more than 2 years) and use the established contraception methods for at least 3 months before the initiation of the trial therapy and 1 month after completion of the trial.
- 8. Men should use adequate contraception during the trial, since signing of the Informed Consent Form and till the trial completion, and for 30 days after the trial completion.
- 9. Ability to understand the presented information on the clinical trial, readiness to comply with the protocol, ability to use the study drugs by oneself and evaluate the symptoms according to VAS (visual analogue scale) or other questionnaires according to the protocol.

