# 4.1.4 Safety and tolerability analysis

AEs incidence will be compared between the trial arms using Pearson's chi-squared test. In case of significant changes, a relative risk will be calculated (with 95% CI).

A tolerability level for every group will be calculated based on the AEs incidence and nature (in accordance with Section 2.3 of this Plan).

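### The rule on pre-existing conditions in Protocol 8.3.4 is inverted as written and contradicts the protocol's own AE definition

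*Protocol*

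**What the plan says.** The sentence at issue is in Protocol 8.3.4 (Documentation on adverse events). It says that conditions or disorders already there before trial therapy starts are "considered to be AEs unless they get worsened after the inclusion in the trial". The next sentence there deals with laboratory findings and is restrictive: "Abnormal laboratory or test results are considered to be AEs only if they evoke clinical signs, are clinically significant, or require therapy". The same section opens by limiting AE documentation to events "occurring after the subject has provided informed consent specific for this trial before completion of the trial".

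Protocol 8.3.1 defines an AE as "any adverse medical event identified in a patient or a clinical trial patient after the use of the drug", whether or not the drug caused it. It says nothing specific about pre-existing conditions.

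The resulting AE data are used in the analysis. Protocol 3.2 lists among the secondary goals "The AEs rate comparison between the trial arms". Protocol 9.1.4 compares incidences between groups with Fisher's exact test, whereas SAP 4.1.4 states: "AEs incidence will be compared between the trial arms using Pearson's chi-squared test". SAP section 1 says it makes no changes to the protocol, and the SAP has no rule of its own on pre-existing conditions.

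**The concern.** A rule on pre-existing conditions should keep baseline illness out of the AE counts and let deterioration in. As worded, this one does the opposite. It is the operative instruction to sites on what to enter on the AE pages, not background text.

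The trial is exposed to this wording because the organ examined for AEs is the organ that is already diseased. Protocol 5.1 requires "A diagnosis of acute, uncomplicated, inflammatory and infectious condition of the pharynx associated with the inflammation and pain in the throat", and AE evaluation at the site visits draws on examination of the throat and pharynx. Sites therefore need a usable rule for separating the baseline illness from something new or worse. At stake is whether the AE incidences compared between arms describe what happened on treatment.

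**Working it through.** No formula applies. The documents state no AE rate and no prevalence of pre-existing conditions, so there is no figure to reproduce. The check is to set the provisions side by side and apply them to the possible cases.

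**Step 1. Compare the rules for a condition that predates consent.**

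| Course after inclusion | 8.3.4 sentence, read literally | 8.3.1 definition with the 8.3.4 window |
|---|---|---|
| Unchanged or improved | AE | Not an AE: nothing adverse has newly occurred since consent or drug use |
| Worsened | Not an AE | Can be an AE: an adverse symptom, complaint or disease after drug use |

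The two columns disagree in both rows.

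**Step 2. Check the neighbouring wording.** The laboratory sentence directly after it admits a finding only when a condition is met. The sentence on pre-existing conditions admits everything except when a condition is met. The two adjacent rules run in opposite directions.

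**Step 3. Look for a correction elsewhere.** Protocol 8.3.1 to 8.3.5, Protocol 9.1.4, and SAP 2.3, 3.6, 4.1.4 and 5.1 contain no statement of the rule the right way round and no instruction that overrides the sentence.

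**Step 4. Apply the sentence to the index disease.** Under Protocol 5.1 every subject has it at entry, with first signs before inclusion. It is therefore a pre-existing condition in every subject. Taken literally, each subject whose throat disease stays the same or improves has an AE, and a subject whose throat disease worsens does not have one on that account. AE incidence would approach 100% in both arms.

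**Step 5. Consequence for the comparison.** Two incidences both close to 100% leave a test on AE proportions little to distinguish, whether it is Fisher's exact or Pearson's chi-squared. From this source alone, an arm with more worsening would show fewer AEs, not more.

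**The case against.** The strongest reply is that the sentence does not stand alone and is probably a slip of drafting or translation.

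- **Worsening has other routes into the record.** The 8.3.1 definition is broad enough to cover it. Protocol 4.2.4.5 provides for an unscheduled visit on deterioration, with both TSS and AE evaluation required. Protocol 8.3.5 requires every SAE to be reported within 24 hours.
- **Stable conditions have their own place.** Medical history is taken at entry and SAP Table 15 lists concomitant diseases. SAP Tables 21 and 22 are titled for events after the start of therapy.
- **The main conclusion is untouched.** SAP section 4 rests non-inferiority on the primary parameter alone and treats the safety parameters as being of research interest.

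Much of this stands, and it limits what can be claimed. A reader might infer that worsening would go entirely unrecorded. The documents do not support that, because the routes above remain open. A reader might also want to put a figure on the inflation of AE rates. Any such figure would need an assumed prevalence that neither document supplies. A modest assumed rise would also be at odds with Step 4, where the literal rule reaches nearly everyone. How sites would actually read the sentence is likewise unknown.

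The reply does not remove the error. The documents cannot confirm a slip. A table title is not a stated filter, and it cannot restore a worsening that was never entered. Listing a condition as concomitant disease does not stop a site from also recording it as an AE, as 8.3.4 instructs. The other provisions show that the protocol contradicts itself; they do not say which instruction a site should follow.

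**Conclusion.** The point holds as a wrong and self-contradictory recording rule. The sentence in Protocol 8.3.4 is inverted on its face, it conflicts with 8.3.1 and with the collection window in its own section, and nothing in either document corrects it. It needs to be put right because it feeds a stated secondary goal and a planned between-arm test.

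The size of the effect cannot be computed from the documents. The near-100% incidence is the logical end point of literal application to the index disease, not a forecast of what sites would record. The conclusion rests only on the wording and on the inclusion criterion that gives every subject a pre-existing throat condition. It affects the AE data only. The primary endpoint, the non-inferiority margin and the sample size do not depend on it.

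**What to change.** Amend the sentence in Protocol 8.3.4 to read along these lines: *conditions present before the start of trial therapy are not considered AEs unless they worsen after inclusion, in which case the worsening is recorded as an AE.* Say explicitly that this applies to the index throat disease. Carry the same wording into the eCRF completion instructions and site training, and state the matching counting rule in SAP 4.1.4, so that Tables 21 to 23 rest on a defined filter and not on a title. If AE data have already been collected, reconcile the AE entries against medical history and concomitant diseases before database lock.

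The change to the sentence is small, but a note to sites is not enough. Protocol 11.2 treats even a formal clarification of wording as an amendment, which needs approval by the sponsor, the regulatory authorities and the ethics committees, and the investigator's signature. No change to the design, sample size or primary analysis follows.

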#### AE in the interval between signing of informed consent and administration of the first dose

Any AEs, which occurred in the interval after signing of informed consent specific for this trial and before administration of the first dose, should be documented as screening period events. Moreover, the results of evaluation of the association with the study drug should be documented as follows: "study drug was not administered yet".

# AE after the first dose of the study drug

The Investigator should follow up all the AEs occurred since the first intake of the drug and during the trial, till the last visit of the subject when the event outcome is evaluated for the last time with further recording in eCRF.

# SAEs not resolved as at the last visit

If SAE is not resolved as at the last visit, the Investigator should follow up the subject till SAE resolution or stabilization/shift to a permanent stage (for SAEs with a suspected relation to the study drugs) or during up to 30 days since the last visit for SAEs without suspected relation to the study drugs.

The Investigator must report on the SAE follow up as per the Reports on SAEs, Section 8.8.5. below.

#### SAEs registered after the last visit

At the last visit, the Investigator should instruct each subject to report on any new SAEs (outside a follow-up period according to the protocol) which, in the subject's opinion, might be associated with the study drugs. The Investigator must inform recipients on SAR as per the Reports on SAEs, Section 8.3.5. below.

#### Clinically relevant abnormal laboratory results at the last visit

The Investigator must document the clinically significant, abnormal laboratory results revealed at the last visit as AEs even without any relation with the specific study drug.

#### 8.3.5 Reports on SAEs

The Investigator must immediately (not later than 24 hours since the receipt of data on SAEs) report any SAEs even in case the Investigator considers these SAEs not related to the study drugs.

The Investigator must use Novartis Serious Adverse Event Report Form to report on SAE for initial or subsequent reporting. The form should be forwarded by fax or email to LPPV with a copy to a manager responsible for the trial (Sponsor/CRO) using the contact information given in a table below.

The Investigator must forward all the updates/new information in a separate Serious Adverse Event Report Form as a follow-up regarding the previously reported SAE. Such information must dwell on recovery or continuation of SAE, diagnosis (if any), therapy details (if any), continuation or discontinuation of that subject from the trial.

Repeated episodes, complications, or progression of the initial SAE should be reported as a follow-up for the original episode, irrespective of the event time.

Any new SAE, which is considered as completely unrelated to previously reported one, shall be reported as a new and separate event.

The Investigator should answer any questions from LPPV, CRO, or Sponsor regarding SAEs reporting within 24 hours.

For more detailed information, refer to the Quick Reference Guide for Completing the SAE Form.

The Investigator should keep the notifications on information delivery to all the recipients in a separate file.

# **Contact information for SAE reporting**

# Notification of the Investigators and the 6-month line listings

If a serious adverse drug reaction (ADR) is not listed in the reference safety information (e.g., SMPC, Investigator's Brochure), the Sponsor may request for an urgent additional information from the Investigator for reporting to the health authorities.

The Sponsor is entitled to, where applicable, forward notifications for the Investigators and the 6month line listings of SUSARs (not previously reported) to all the investigators associated with any trial of the same study drug.

The Investigator or CRO (as envisaged in the trial agreement) must submit the notifications for Investigators and the 6-month line listings, if applicable, to Local Ethics Committees (LEC)/Ethics Councils. CRO must submit the notifications for Investigators and the 6-month line listings, if applicable, to the Ethics Council under the Ministry of Health of Russia.

**Reporting to health authorities** 

The Sponsor shall submit all the reports to relevant regulatory authorities within the specified timelines.

#### **Training of investigators**

By signing the trial protocol, the Principal Investigator confirms that he/she has passed the training held by CRO and got familiarized with the Sponsor's requirements and his/her responsibilities on reporting the AEs/SAEs and pregnancies as defined in the trial protocol.

#### 8.4 Pregnancy cases

The Investigator must immediately (not later than 24 hours since the receipt of information on pregnancy) inform the Sponsor/LPPV with a copy to a manager responsible for the trial (Sponsor/CRO) as described in Section 8.3.5 on all the pregnancy cases occurred during the trial. Pregnancy reports are registered since the first intake of the study drug only.

The Investigator must exclude the pregnant subject from the trial immediately; this pregnancy should be monitored to determine its termination, including spontaneous or planned abortion, details on delivery and on presence or absence of any development defects, congenital anomalies, or complications in infant's mother and/or in a newborn.

If the Investigator becomes aware of pregnancy of the sex partner of male participant of the trial, which was started with high probability during participation of this man in the trial (i.e., during exposure of the child's father organism to the drug), these pregnancy cases should be also reported after receipt of informed consent from (expecting) mother.

The pregnancy cases should be registered in the Clinical Trial Pregnancy Form. Additional information about pregnancy should be registered in the same form. Moreover, it must include possible relation of any termination of pregnancy to use of the study drug.

Any SAE noted during pregnancy should be reported using SAE Report Form as described in Section 8.3.4.

For more information, see the Clinical Trial Pregnancy Quick Reference Guide; Novartis document.

